9.7.2 Causal Relationship of Adverse Events to Investigational Study Drugs

Medical judgment should be used to determine the cause of the AE considering all relevant factors such as, but not limited to, the underlying study indication, coexisting disease, concomitant medication, relevant history, pattern of the AE, temporal relationship to the study medication, dechallenge or rechallenge.

Not Related

- An AE that is clearly due to extraneous causes (eg, concurrent disease, concomitant medications, disease under study);
- It does not correspond to a reasonable temporal sequence from administration of study drug;
- It does not correspond to a known pattern of response to study drug;
- It does not reappear or worsen when study drug is restarted;
- An alternative explanation is likely but not clearly identifiable.

Possibly Related

- An AE that is difficult to assign to alternative causes;
- It corresponds to a strong or reasonable temporal sequence from administration of study drug;
- It could not be reasonably explained by the patient's clinical state, concurrent disease, or other concomitant therapy administered to the patient;
- It corresponds to a known response pattern to study drug;
- It is confirmed with a positive rechallenge or supporting laboratory data.

9.7.3 Outcome and Action Taken

The Investigator will record the action taken and outcome for each AE according to the following criteria:

- Action Taken with Study Drug:
 - None;
 - Rociletinib dose reduced;
 - Rociletinib temporarily interrupted;
 - Rociletinib permanently discontinued;
 - MPDL3280A temporarily interrupted;
 - MPDL3280A permanently discontinued;
 - Other (specify).
- Outcome:
 - Recovered;
 - Recovered with sequelae;
 - Improved;
 - Ongoing;
 - Death;
 - Lost to follow up.

9.8 Follow-Up of AEs and SAEs

All AEs occurring during the study are to be followed up in accordance with good medical practice until resolved; judged no longer clinically significant; or, if a chronic condition, until fully characterized through 28 days after the last dose of rociletinib and/or MPDL3280A. All ongoing AEs related to study treatment, all SAEs, and all protocol-defined events of special interest (Section 9.6) will be followed until the event has resolved to baseline grade, the event is assessed by the Investigator as stable, new anticancer treatment is initiated, the patient is lost to

follow up, the patient withdraws consent, or it is determined that the study treatment or participation is not the cause of the adverse event.

9.9 Regulatory Aspects of SAE Reporting

All SAEs, regardless of relationship to study drug, must be reported to the safety contract research organization (CRO) within 24 hours of knowledge of the event, according to the procedures below. It is important that the Investigator provide an assessment of relationship of the SAE to study treatment at the time of the initial report. The Clinical Trial Serious Adverse Event Report Form must be used for reporting SAEs.

While not considered an SAE, pregnancy occurring in a female patient or in the female partner of a male patient must also be reported to the CRO as soon as the event is known by the clinical site. If the pregnancy occurs in a female patient, study drug should be stopped immediately. Notification to the CRO should take place via facsimile or email utilizing the Pregnancy Report Form.

Further details on SAE/pregnancy reporting can be found in the Investigator's file.

The Sponsor or its designee is responsible for submitting reports of AEs associated with the use of the drug that are both serious and unexpected to the US Food and Drug Administration (FDA), according to 21 Code of Federal Regulations (CFR) 312.32; to the Japanese Pharmaceuticals and Medical Devices Agency; to the European regulatory authorities according to the European Commission Clinical Trials Directive (2001/20/EC); and to other regulatory authorities, according to national law and/or local regulations. All investigators participating in ongoing clinical studies with the study medication will receive copies of these reports for prompt submission to their IRB or IEC. In accordance with the European Commission Clinical Trials Directive (2001/20/EC), the Sponsor or its designee will notify the relevant ethics committees in concerned member states of applicable suspected unexpected serious adverse reactions (SUSARs) as individual notifications or through periodic line listings. The Sponsor or its designee will submit all safety updates and periodic reports to the regulatory authorities as required by applicable regulatory requirements.

10 STATISTICAL METHODS

10.1 Analysis Populations

The following analysis populations are defined for the study:

Tumor evaluable population—all patients who received at least one dose of rociletinib or MPDL3280A, have at least one measureable tumor lesion at baseline, and have at least one post-baseline tumor assessment as determined by the Investigator.

Safety population—all patients who have received at least one dose of rociletinib or MPDL3280A.

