3.2 Dose Finding Phase (Phase 1)

The Dose Finding Phase will be conducted with patients who have progressed after at least 12 weeks of treatment with a prior first- or second-generation EGFR TKI (ie, erlotinib, gefitinib, afatanib), regardless of T790M mutation status. The Dose Finding Phase will be used to determine the MTD or MAD and RP2D of the combination of rociletinib and MPDL3280A, and to evaluate the safety, tolerability, and PK profile of the combination treatment. The Dose Finding Phase will include a 7-day Run-in-Period of rociletinib monotherapy prior to the initiation of combination treatment. Patients will receive daily oral BID doses of rociletinib at the Dosing Cohort-defined dose level (Section 3.2.2). Patients who experience an AE that requires a reduction or more than 48-hour delay in dose of rociletinib during the Run-in-Period will not go on to receive the combination of rociletinib and MPDL3280A, but will remain on study to receive rociletinib monotherapy; an additional patient will be enrolled as a replacement for inclusion in the same Dosing Cohort.

For the Dose Finding Phase, Cycle 1 will begin with the initiation of combination treatment following a successful completion of the Run-in-Period and will be used for the determination of DLTs. Patients will continue to receive daily oral BID doses of rociletinib (at the Dosing Cohort-defined dose level) and IV doses of MPDL3280A on Day 1 of each cycle, in consecutive 21-day cycles. Thereafter, treatment and monitoring of patients will be conducted in 21-day treatment cycles. Patients will be evaluated regularly for safety, PK, efficacy and pharmacodynamics according to the Schedule of Assessments (see Table 1). For further details on the planned assessments and analyses of safety, PK, efficacy and pharmacodynamics, please refer to Sections 8.4.2-8.4.5.

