5.4 Blinding/Masking of Treatment

This is an open-label study; the investigational product will not be blinded or masked. All patients enrolled will receive PO rociletinib and IV MPDL3280A.

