5.7.2 Phase 1 – Run-in-Period

Rociletinib monotherapy will be administered orally BID during the 7-day Run-in-Period. Dose reductions of rociletinib during the Run-in-Period are not allowed for reasons other than a DLT. Dose delays of rociletinib for up to 48 hours for toxicity management is allowed. Any patient who experiences an AE(s) that requires either a delay of treatment for more than a total of 48 hours or a dose reduction during the 7-day Run-in Period of rociletinib monotherapy will not be eligible for combination therapy. Such a patient will only receive monotherapy rociletinib for the duration of participation in the study.

5.7.3 Phase 1 – Cycle 1

The first dose of MPDL3280A at 1200 mg will be administered by IV on C1D1. Dose reductions of rociletinib are not allowed for reasons other than a DLT or a decision by the CSC based on emerging safety data. Dose delays of rociletinib are not allowed for reasons other than toxicity. Patients are eligible for safety and DLT evaluation of the cohort if they receive at least 75% of the planned total dose of each study drug within Cycle 1 or they experience a DLT at any time during Cycle 1.

5.7.4 Beyond DLT Assessment (Phase 1 – Cycle 2+ and Phase 2 – All Cycles)

For patients who experience a toxicity that is equivalent to a DLT – If the toxicity is assessed as being related to rociletinib, the next dose of rociletinib should be held until resolution of the toxicity to Grade 1 or to the baseline level (if severity > Grade 1 at baseline) and then reduced to the next dose level of rociletinib (Table 7), unless permanent discontinuation of rociletinib is required per toxicity management guidelines of the protocol (Sections 6.1 and 6.3). If the toxicity is assessed as being related to MPDL3280A, the next dose of MPDL3280A should be held until the toxicity has resolved to Grade 1 or to the baseline level (if severity > Grade 1 at baseline), unless permanent discontinuation of MPDL3280A is required per toxicity management guidelines of the protocol (Sections 6.2 and 6.3). In addition, because there is no available antidote for MPDL3280A and discontinuation of MPDL3280A may not have immediate therapeutic effect, consideration may be given to holding rociletinib doses temporarily even if the toxicity is not attributed to rociletinib.

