10.2.5 Safety Analyses

The safety analyses will be performed using the safety population.

Safety data analysis will be conducted on all patients receiving at least one dose of rociletinib or MPDL3280A. The number and percentage of patients experiencing one or more AEs will be summarized by dose level group, relationship to study drug, and severity. AEs will be coded using MedDRA terminology. Listings of patients who experienced DLT during Cycle 1, dose reductions, dosing interruptions, withdrawal due to an AE, SAEs and/or death will be presented. Laboratory parameters will be summarized using descriptive statistics, by post-dosing shifts relative to baseline, and data listings of clinically significant abnormalities. Vital signs, ECOG performance status, and ECG data will be summarized by changes from baseline values at each dose level using descriptive statistics.

A mTPI method will be used to identify the MTD or MAD and the RP2D. The mTPI, a model-based approach that has a pre-specified decision matrix that recommends escalating, reducing or maintaining the same dose or stopping dose escalation, based on the toxicities observed in the dose level under evaluation, reduces the risk of exposing patients to doses above the MTD compared with 3+3 design in which there is a 71% chance of escalation if the true but unknown rate of DLT is 20% and less than 50% chance of escalation if the true but unknown rate of DLT is higher than 30%.

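### Phase 1 adverse event and efficacy summaries mix rociletinib-only and combination exposure, because neither the analysis populations nor the adverse event window requires MPDL3280A

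*Combined protocol and SAP*

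**What the plan says.** **Who is analysed.** Section 10.1 defines the safety population as "all patients who have received at least one dose of rociletinib or MPDL3280A". The tumor evaluable population is "all patients who received at least one dose of rociletinib or MPDL3280A, have at least one measureable tumor lesion at baseline", with at least one post-baseline assessment. Section 10.2.5 repeats the either-drug rule for safety: "Safety data analysis will be conducted on all patients receiving at least one dose of rociletinib or MPDL3280A".

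**Who fails the run-in.** Phase 1 opens with 7 days of rociletinib alone. Under Section 3.2, a patient whose adverse event in that week requires a dose reduction or a delay of more than 48 hours does not go on to the combination "but will remain on study to receive rociletinib monotherapy". Section 5.7.2 adds: "Such a patient will only receive monotherapy rociletinib for the duration of participation in the study". Section 3.2 also provides that "an additional patient will be enrolled as a replacement for inclusion in the same Dosing Cohort".

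**What is counted.** Section 10.2.5.2 opens the treatment-emergent window at the first dose of either drug, which in Phase 1 is run-in Day 1. It tabulates events by dose group and study phase. Laboratory and vital-sign baselines also precede the run-in (Sections 10.2.5.3 and 10.2.5.4).

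**What the summaries are for.** The Phase 1 primary objective concerns the safety and tolerability of the combination (Section 2.1.1). Treatment-emergent events are a primary endpoint (Section 2.2.1). Preliminary efficacy of the combination is a Phase 1 secondary objective (Section 2.1.2).

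**A conflicting statement.** Section 5.4 says: "All patients enrolled will receive PO rociletinib and IV MPDL3280A".

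**The concern.** The Phase 1 objectives are about two drugs given together, but no analysis population in Section 10.1 matches them. Two kinds of non-combination data enter the Phase 1 summaries: all data from patients who never receive MPDL3280A, and run-in events from everyone else.

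The distortion runs in both directions. A run-in failure cannot have an event caused by MPDL3280A but sits in the denominator, so rates of immune-related events caused by that drug are diluted. The same patient has, by definition, an event that led to a rociletinib reduction or delay, so general tolerability rates are raised. In the efficacy summaries, a response or progression on rociletinib alone would count toward a description of the combination. A reader of the Phase 1 tables could not separate these parts.

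**Working it through.** The plan states no figure to reproduce. The check is first a comparison of definitions, then illustrative arithmetic.

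**Tracing one run-in failure through the plan**

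- Safety population: included, having received rociletinib (Section 10.1).
- Tumor evaluable population: included once there is a measurable baseline lesion and one post-baseline assessment (Section 10.1).
- Treatment-emergent event tables: included from run-in Day 1, with no monotherapy group and no period split (Section 10.2.5.2).
- DLT evaluation: excluded. DLTs are determined in the first 21 days of combination treatment (Section 3.2.1), and evaluability needs at least 75% of each drug in Cycle 1 or a Cycle 1 DLT (Sections 3.2.2 and 5.7.3). Section 5.7.2 uses the term DLT for the run-in, but Section 3.2.1 confines the determination to combination treatment.
- MPDL3280A PK, anti-therapeutic antibody and TBNK samples: excluded. The notes to Table 1 restrict these to patients with at least one dose of MPDL3280A.

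The protocol therefore recognises this subgroup for dose finding and sampling, but not in the safety and efficacy populations. Phase 2 has no run-in (Section 3.3) and cannot produce such patients.

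**Illustrative size**

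Let *f* be the run-in failure fraction. It is not in the documents, so 5% to 30% is assumed. Take 18 patients enrolled, the Phase 1 maximum in Section 3.2.2, which does not say whether run-in failures count toward it. Assume a true rate of 20% among combination-treated patients for each type of event.

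- Expected monotherapy-only patients: 18*f*.
- Chance of at least one: 1 − (1 − *f*)^18.
- Reported rate of an event caused only by MPDL3280A: 0.20(1 − *f*).
- Reported rate of events leading to interruption or reduction, where every run-in failure counts: 0.20(1 − *f*) + *f*.

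| *f* | Expected number | At least one | MPDL3280A-only event | Interruption or reduction |
|---|---|---|---|---|
| 5% | 0.9 | 60% | 19% | 24% |
| 10% | 1.8 | 85% | 18% | 28% |
| 20% | 3.6 | 98% | 16% | 36% |
| 30% | 5.4 | 99.8% | 14% | 44% |

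If the 18 are all combination-treated and failures come on top, the safety population would be 18/(1 − *f*), or about 18.9, 20.0, 22.5 and 25.7. In a single small cohort, 2/6 (33%) becomes 2/8 (25%) with two run-in failures in the same column.

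**Run-in events in patients who do go on**

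Table 4 gives treatment-related hyperglycemia in 11/18 = 61.1% at 500 mg BID (HBr) on rociletinib alone. Section 6.1.2 places onset generally in the first 3 weeks, which include the run-in. If 25% to 50% of those events arose in week 1 (an assumed share) and the rate carried over, 0.611 × 0.25 = 15% to 0.611 × 0.50 = 31% of patients would have a treatment-emergent event before any MPDL3280A.

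**The case against.** An any-dose safety population is conventional, and the plan protects the parts that drive dose decisions. DLTs are themselves a Phase 1 primary endpoint, restricted to combination treatment and given their own table. Phase 1 efficacy is only preliminary. All of this stands. A reader might infer that the dose-finding decisions are contaminated or that the Phase 2 response rate is affected; the documents support neither.

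Pooling is also a consequence of omission, not an instruction. Dose group is never defined, Section 10.2.1 says only that data are shown by dose cohort as appropriate, and enrolling a replacement in the same cohort could mean that the failed patient leaves it. Sections 10.2.4 to 10.2.4.2.4 specify no dose-group columns for response or PFS. This limits what can be said about table layout. It does not remove these patients from either population, nor run-in events from the treatment-emergent window.

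A reader might also infer that the mixture would be undetectable. That goes too far: Section 10.2.5.1 summarises exposure for each drug, and Section 9.7 has causality assessed for each drug. The event tables themselves still do not separate the groups, and the relationship summary in Section 10.2.5.2 is for the oral drug only.

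The size is assumed, and small shifts sit well inside sampling error: 3/18 (17%) against 3/21 (14%) have exact 95% intervals of 4% to 41% and 3% to 36%. That tempers the urgency. The mismatch is nonetheless one of definition and can be removed in advance.

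Finally, replacing the any-dose set with combination-treated patients, and counting events only from C1D1, would bring its own bias. It selects patients who tolerated a week of rociletinib and drops run-in toxicity that persists into combination dosing. This stands, and it is why the any-dose set should stay.

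**Conclusion.** The concern holds for Phase 1 only. As defined, the Phase 1 treatment-emergent event tables and preliminary efficacy summaries describe a mix of rociletinib monotherapy and combination exposure, while the objectives they serve concern the combination. It would be too strong to say that they do not describe the combination at all: patients who pass the run-in contribute their full combination experience.

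The size cannot be determined from the documents. Under the assumed failure rates, rates of events caused only by MPDL3280A are understated by 5% to 30% in relative terms, and rates of interruption or reduction are overstated. The conclusion rests on Sections 3.2 and 5.7.2 being followed as written. Section 5.4 contradicts them, but it is a statement about blinding; a reader might take it as the premise of the analysis plan, and nothing in Section 10 says so.

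**What to change.** - Keep the any-dose safety population in Section 10.1.
- Add a Phase 1 combination-treated set, meaning at least one dose of MPDL3280A, and use it for the event and efficacy summaries that are meant to describe the combination.
- Show run-in failures in a separate rociletinib-monotherapy column, and define dose group accordingly.
- Split Phase 1 treatment-emergent events by onset, run-in against from C1D1, and still show run-in-onset events that continue or worsen after C1D1.
- Reconcile Section 5.4 with Sections 3.2 and 5.7.2.

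The cost is one extra population and one extra column from data already collected. The combination-treated set is selected for tolerating the 7-day run-in, and this should be stated wherever it is compared with Phase 2, where both drugs start together.

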10.2 Statistical Methods

10.2.1 General Considerations

Data will be summarized using descriptive statistics (number of patients, mean, median, standard deviation, minimum, and maximum) for continuous variables and using frequencies and percentages for discrete variables. Data will be presented by dose cohorts, as appropriate.

Kaplan-Meier methodology will be used to summarize time to event variables.

All data will be used to their maximum possible extent but without any imputations for missing data.

All statistical analyses will be conducted with the Statistical Analysis Software (SAS[®]) system.

10.2.2 Patient Disposition

The frequency and percentage of patients in each analysis population will be presented. The primary reason for discontinuation of rociletinib and/or MPDL3280A will be summarized.

10.2.3 Baseline Characteristics

Baseline characteristics and demographic data will be summarized for the safety population.

10.2.4 Efficacy Analyses

The efficacy endpoints of ORR, DoR, DCR, and PFS will be evaluated using RECIST v1.1 (Appendix A:) and modified RECIST incorporating irRC (Appendix B). Efficacy endpoints evaluated by the Investigator will be presented for the subgroup of patients determined to be tumor evaluable by the Investigator.

Progression-free survival and OS will also be presented for the safety population.

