10.2.4.1 Primary Endpoint (Phase 2)

The primary endpoint of the Dose Expansion Phase (Phase 2) of the study is ORR per RECIST as assessed by the Investigator.

The ORR is the best overall response recorded from the start of the treatment until disease progression or recurrence.

The frequency and percentages of patients with a best overall response of CR, PR, stable disease (SD), or PD will be summarized. The confirmed response rate will also be summarized with frequencies and percentages.

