Progressive Disease	At least a 20% increase in the sum of the LD of target lesions, taking as reference the smallest sum on study (this includes the baseline sum if that is the smallest on study). In addition to the relative increase of 20%, the sum must also demonstrate an absolute increase of at least 5 mm. The appearance of one or more new lesions is also considered progression.

Evaluation of Non-Target Lesions

Complete Response	Disappearance of all non-target lesions and normalization of tumor marker level.
Stable Disease/Incomplete Response	Persistence of one or more non-target lesion(s) or/and maintenance of tumor marker level above the normal limits.
Progressive Disease	Appearance of one or more new lesions and/or unequivocal progression of existing non-target lesions.

If tumor markers are initially above the institutional ULN, they must normalize for a patient to be considered a complete *responder*.

Evaluation of Best Overall Response

The best overall response is the best response recorded from the start of the treatment until disease progression/recurrence (taking as reference for PD the smallest measurements recorded since the treatment started). The patient's best response assignment will depend on the achievement of both measurement and confirmation criteria.

Time Point Response

A response assessment will occur at the protocol-specified time points. The tables below provide a summary of the overall response status calculation at each time point for patients who have measureable and non-measureable disease (non-target disease only).

Target Lesions	Non-target Lesions	New Lesions	Overall Response		
CR	CR	No	CR		
CR	Non-CR/non-PD	No	PR		
CR	Not evaluated	No	PR		
PR	Non-PD or not evaluated	No	PR		
SD	Non-PD or not evaluated	No	SD		
Not Evaluated	Non-PD	No	NE PD		
PD	Any	Yes or No			
Any	PD	Yes or No	PD		
Any	Any	Yes	PD		

Time point Response: Patients with Target (± non-target) Disease

CR, complete response; PD, progressive disease; PR, partial response; SD, stable disease; NE, Not evaluable.

Evaluation of Best Overall Response When Confirmation of CR and PR Required

Overall Response : First Time Point	Overall Response: Subsequent Time Point	Best Overall Response
CR	CR	CR
CR	PR	SD, PD or PR ^a
CR	SD	SD provided minimum criteria for SD duration met, otherwise, PD
CR	PD	SD provided minimum criteria for SD duration met, otherwise, PD
CR	NE	SD provided minimum criteria for SD duration met, otherwise, NE
PR	CR	PR
PR	PR	PR
PR	SD	SD

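### The Phase 2 primary ORR is planned only for tumor-evaluable patients, so treated patients who are never scanned leave the denominator

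*Combined protocol and SAP*

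**What the plan says.** **Endpoint.** Sections 2.2.1 and 10.2.4.1 make investigator-assessed ORR per RECIST v1.1 the Phase 2 primary endpoint. Section 2.1.1 sets the objective separately for Groups A and B.

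**Population.** Section 10.2.4 states: "Efficacy endpoints evaluated by the Investigator will be presented for the subgroup of patients determined to be tumor evaluable by the Investigator". Under Section 10.1, the tumor-evaluable set consists of patients who took a dose of either drug, had a measurable lesion at baseline "and have at least one post-baseline tumor assessment as determined by the Investigator". The safety population needs only a dose. The one all-treated efficacy presentation in Section 10.2.4 is: "Progression-free survival and OS will also be presented for the safety population".

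**Display.** Section 10.2.4.1 names no other denominator and tabulates best response as CR, PR, SD or PD. Section 10.2.1 excludes imputation of missing data. Section 10.2.2 adds: "The frequency and percentage of patients in each analysis population will be presented".

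**Confirmation.** Section 10.2.4.1 says: "The confirmed response rate will also be summarized with frequencies and percentages". Appendix A says that the patient's "best response assignment will depend on the achievement of both measurement and confirmation criteria".

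**The concern.** Membership of the tumor-evaluable set depends on something that happens after treatment starts. Section 8.4.3.1 puts the first scheduled scan at the end of Cycle 2, about week 6. A patient who dies, withdraws consent or misses the end-of-treatment scan before any post-baseline assessment is removed from the ORR. Such a patient cannot be a responder, so each removal shrinks the denominator and leaves the numerator alone.

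At stake is what the primary estimate means. Phase 2 has no control arm in which the same loss would also occur. Section 10.3 sets the combination against single-agent reference rates of 50% (Group A and T790M+) and 30% (T790M–). Two secondary endpoints get an all-treated presentation and the primary endpoint does not.

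A smaller issue is that Section 10.2.4.1 can be read as making the main rate unconfirmed, whereas Appendix A makes best response depend on confirmation.

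**Working it through.** The plan gives no expected non-evaluable share, precision target or derivation of the group sizes for ORR, so it has no figure of its own to reproduce here.

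**Inputs from the documents.** About 25 patients in Group A and about 50 in Group B, of whom about 30 are expected to be T790M+ and 20 T790M– (Section 10.3). Reference rates are 50%, 50% and 30%. Measurable disease is an inclusion criterion (Section 4.2) and waivers are ruled out (Section 4.5), so the condition that matters in practice is the post-baseline assessment.

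**Input assumed.** The share *m* of treated patients never scanned is 4% to 12%, that is 1 to 3 of 25.

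**Step 1, direction.** With *x* responders, *n* treated and *k* unscanned, the planned rate is *x*/(*n* − *k*) and the all-treated rate is *x*/*n*. Since *x*/(*n* − *k*) ≥ *x*/*n*, the planned rate is never the lower of the two.

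**Step 2, rates.** Reported rate = *p*/(1 − *m*), where *p* is the all-treated rate.

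| All-treated *p* | *m* = 4% | *m* = 8% | *m* = 12% |
|---|---|---|---|
| 50% | 52.1% | 54.3% | 56.8% |
| 30% | 31.25% | 32.6% | 34.1% |

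**Step 3, counts.**

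| Set | All treated | Unscanned | As planned |
|---|---|---|---|
| Group A | 12/25 = 48.0% | 1 | 12/24 = 50.0% |
| Group A | 12/25 = 48.0% | 3 | 12/22 = 54.5% |
| T790M+ | 15/30 = 50.0% | 2 | 15/28 = 53.6% |
| T790M– | 6/20 = 30.0% | 2 | 6/18 = 33.3% |

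The exact (Clopper-Pearson) 95% interval is 27.8% to 68.7% for 12/25 and 32.2% to 75.6% for 12/22. The shift is small against that width, but it does not average out.

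**Step 4, not-evaluable best response.** Appendix A can assign NE to a scanned patient. For an initial PR or CR followed by an NE assessment, its entry is "SD provided minimum criteria for SD duration met, otherwise, NE". Such a patient has had a post-baseline assessment and so stays in the Section 10.1 set. The Section 10.2.4.1 table simply has no row for the patient.

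**Step 5, futility looks.** The plan's rules give P(0/5 at 50%) = 0.5^5 = 3.1% and P(0/9 at 30%) = 0.7^9 = 4.0%. Assume that 10% to 20% of recorded responses are not confirmed (*u*).

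- If 50% and 30% are confirmed rates, looking at unconfirmed responses gives (1 − *p*/(1 − *u*))^*n*: 3.1% falls to 1.7–0.7%, and 4.0% to 2.6–1.5%.
- If they are unconfirmed rates, looking at confirmed responses gives (1 − *p*(1 − *u*))^*n*: 3.1% rises to 5.0–7.8%, and 4.0% to 5.9–8.5%.

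Section 10.3 does not say which kind of rate it uses, so neither direction can be claimed.

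**The case against.** The best defence is that little turns on this. Phase 2 ORR is descriptive, with no test, success threshold or precision target, and the futility rules only permit stopping. A response-evaluable set fixed in advance is a defensible choice for expansion groups of 25 and 50. That holds, and it limits the weight of the point. It does not explain why the primary endpoint lacks the all-treated presentation given to PFS and OS.

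The loss may also be small. Section 8.4.3.1 schedules an end-of-treatment scan, and Section 11.1 describes follow-up for progression every 8 weeks after treatment stops. Entry requires ECOG 0 or 1 and a life expectancy of at least 3 months. So it would be wrong to infer that every early stopper is lost. However, Section 8.4.3.1 has tumor assessments only until all treatment is discontinued, so it needs reconciling with Section 11.1. Neither route reaches a patient who dies or withdraws before a scan.

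A reader could also rebuild the all-treated rate by dividing CR + PR from Section 10.2.4.1 by the safety-population count from Section 10.2.2. That largely works, but the result is not planned. For the population counts the only stated breakdown is general: "Data will be presented by dose cohorts, as appropriate". It would be too strong to say that ORR itself is not planned by Group, because Sections 2.1.1 and 10.3 treat the Groups separately.

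On confirmation, the sentence about also summarizing a confirmed rate has no counterpart in Section 10.2.4.2.1, where Appendix B already builds confirmation into CR and PR. Appendix A's table is headed as applying when confirmation is required. This favours reading the main RECIST v1.1 rate as unconfirmed. It does not settle the matter, because Section 2.2.1 ties the endpoint to Appendix A and its general sentence on best response.

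**Conclusion.** The denominator point stands and should be fixed. Followed as written, the plan drops treated patients who are never scanned from the primary ORR, which can only raise it. The size is unknown. With an assumed 4% to 12% unscanned, the increase is about 1 to 7 percentage points at all-treated rates of 30% to 50%, within sampling error for groups of this size.

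Three stronger readings are not supported:

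- **Scanned patients with an NE best response leave the denominator.** Section 10.1 keeps them in; only the table row is missing.
- **An error rate or a go decision is compromised.** No test or threshold is attached to ORR.
- **The futility rules are biased in a known direction.** Step 5 shows that the sign depends on a definition that Section 10.3 does not give.

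The confirmation issue is a real tension between Section 10.2.4.1 and Appendix A. Both rates will be reported, so it is a labelling matter and secondary to the denominator.

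**What to change.** - **Sections 10.2.4 and 10.2.4.1:** make the primary result the ORR for Group A and for Group B in all Phase 2 patients who took a dose of either drug, counting patients without a post-baseline scan as non-responders. Keep the tumor-evaluable rate as supportive. Add an NE row to the best-response table.
- **Section 10.2.4.1 and Appendix A:** state which rate is primary (the confirmed one, if Appendix A is followed) and label the other as supportive.
- **Section 10.3:** apply that same response definition, and one named patient set, to the futility looks.
- **Sections 8.4.3.1 and 11.1:** reconcile what they say about tumor assessment after treatment stops.

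The cost is wording and one table row. The safety population and the confirmatory scans are already in the plan. The downside is a slightly lower reported ORR and possibly a less like-for-like comparison with single-agent rates, whose definition the documents do not give. Keeping the tumor-evaluable rate beside the primary one limits this.
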